4.2.1.3 Rationale for Study Population (SOF + RBV and SOF + peg-IFN/RBV failures)

TE subjects who have failed SOF with or without RBV are eligible for this **study as it is highly unlikely they will respond any differently to EBR/GZR than other IFN/RBV failures**. Given that SOF utilizes a mechanism of action distinct from either EBR or GZR, RAVs selected by SOF maintain full susceptibility to EBR and GZR. Furthermore, to date, identification of SOF RAVs in GT4 subjects failing either SOF/RBV or SOF/peg-IFN/RBV is exceedingly rare. Of the 17 patients who did not achieve a SVR₁₂ in the Egyptian GT4 study [17] and the one failure in the NEUTRINO study [18], none had the signature RAV for SOF, the S282T, suggesting that GT4 subjects who fail these SOF/RBV +/-peg-IFN will have future treatment options in the unlikely event they fail EBR/GZR. The rationale for excluding all other DAA-based failures is that treatment with any DAA-including regimen other than SOF + RBV or SOF + peg-IFN would have included either an NS5A or NS3 inhibitor, thus those who failed these regimens are at increased risk for baseline resistance to either EBR and/or GZR.

4.2.1.4 Rationale for Study Population (Compensated Cirrhotic Patients)

Compensated cirrhotic patients are included given that they are at the highest risk of developing complications from liver disease [23] and are considered to be a high priority for treatment in the French guidelines. SVR confers numerous clinical benefits including improvement in mortality, reduction in HCC and reduction in hepatic decompensation [12], hence the need to treat those who are at the greatest risk for developing these outcomes. Current treatment recommendations for GT4 cirrhotic patients (Table 4) include either 24-week regimens or 12-week regimens that include RBV. There are no 12-week RBV free regimens included in the current French treatment guidelines for cirrhotic GT4 patients and this study proposes to evaluate such a regimen in both TE and TN cirrhotic patients. In addition to increasing pill burden, RBV is associated with toxicities such as anemia, its use typically requires additional monitoring, and administration may not be optimal in the setting of significant comorbidities such as cardiac and renal disease. An integrated analysis of 402 compensated cirrhotic patients with HCV GT1, GT4, or GT6 infection treated with EBR and GZR ± RBV for 12 to 18 weeks demonstrated comparable efficacy to what is seen in non-cirrhotic subjects. A small number of GT4 subjects were included in this analysis and as seen in Table 3, 6/6 TN GT4 cirrhotics and 4/5 TE GT4 cirrhotics achieved SVR₁₂. The overall efficacy of all compensated cirrhotic GT1, GT4 and GT6 (SVR₁₂) TN and TE subjects treated with 12 weeks of EBR/GZR was 98% (135/138) and 89% (48/54), respectively. Among TE cirrhotics, 2 of the 6 subjects failed to attain a SVR due to administrative reasons [24]. These data support inclusion of compensated cirrhotic subjects in the proposed study Arm 2.

4.2.1.5 Rationale for Study Population (HIV Co-infection)

Subjects co-infected with human immunodeficiency virus (HIV) will not be excluded from this trial given that treatment outcomes with DAA-based regimens are no different in HCV mono-infected versus co-infected HCV/HIV patients with preserved immune function [20]. Similar conclusions have been observed in the EBR/GZR clinical program, wherein, HIV co-infected GT1- and GT4-infected subjects had similar high efficacy following EBR/GZR therapy in Phase 3 studies [25]. In the EBR/GZR Phase 3 program, Protocol PN061 treated GT1-, GT4-, and GT6-infected subjects co-infected with HIV with and without cirrhosis [26]. All were treated with a regimen of EBR/GZR without RBV for 12 weeks and the efficacy was 96% (210/218) and was 100% in the 16% of co-infected subjects with cirrhosis. The subject response rate across all demographics, including Black subjects, was similar to the mono-infected subjects. With similar efficacy achieved with EBR/GZR in mono- and co-infected subjects, this trial will co-enroll HIV infected subjects in all treatment arms.

4.2.1.6 Rationale for Sample Size

The sample size for each treatment group in this study (n = 50 in Arm 1 and n = 70 in Arm 2) was selected based on the knowledge of the epidemiology of HCV infection in France. This is an exploratory study with no formal hypotheses thus the sample size is reflective of the number of subjects that are likely to be enrolled in each treatment arm. The current sample size will be used to estimate efficacy and safety of these 2 treatment regimens (refer to Table 17 and Table 18 in Section 8.9).

4.2.2 Rationale for Dose Selection/Regimen/Modification

Dose Selection for EBR

An EBR dose of 50 mg daily (QD) was selected based on a Phase 1b monotherapy study in HCV-infected subjects, EBR PN002, and a Phase 2a dose-ranging study (PN035 Part A), as well as the favorable efficacy and safety profile demonstrated in a large Phase 2/3 program in which approximately 2000 subjects were treated with a dose of EBR (50 mg) including subjects with cirrhosis, HIV co-infection, and prior treatment experience. For detailed information, please refer to the IB.

Dose Selection for GZR

A GZR dose of 100 mg QD was selected based on Phase 2 dose-ranging studies (PN003, PN038) as well as the favorable efficacy and safety profile demonstrated in a large Phase 2/3 program in which approximately 2000 subjects were treated with a dose of GZR (100 mg) including subjects with cirrhosis, HIV co-infection and prior treatment experience. For detailed information, please refer to the IB.

4.2.2.1 Rationale for 8-week Regimen of EBR/GZR in TN GT4 Subjects with F0-F2 Fibrosis (Arm 1)

Preclinical studies demonstrate that the in vitro activity of both EBR and GZR against GT4 is similar to GT1b when assessed in HCV replicon cell-based assays. This work included evaluation of most of the common GT4 subtypes that are associated with clinical disease. For reference, available EBR and GZR in vitro susceptibility data for all GT4 subtypes that were identified from French patients in the study discussed in Section 4.1.1.1 [9] are summarized in [Table 5](#) and [Table 6](#) with GT1b EC50 provided for comparison.

Table 5 EBR and GZR *In Vitro* Susceptibility Data for All GT4 Subtypes Identified from French Patients

GT4 Subtype	Frequency of GT4 subtype among 81 isolates from France sequenced in ref [9] n (%)	Number of GT4 subtype replicons assayed	Range of GZR EC ₅₀ (nM)	GZR EC ₅₀ for GT1b in Con 1 replicon for reference (nM ± SD)
4a	41 (50.6%)	1	0.3	0.5 ± 0.3
4d	17 (21%)	1	0.6	0.5 ± 0.3
4f	10 (12.3 %)	0	n/a	0.5 ± 0.3
4k	3 (3.7%)	0	n/a	0.5 ± 0.3
4g	2 (2.5%)	2	0.15-0.33	0.5 ±-0.3
4c	2 (2.5%)	0	n/a	0.5 ±-0.3
4q	2 (2.5%)	0	n/a	0.5 ±-0.3
4t	2 (2.5%)	0	n/a	0.5 ±-0.3
4n	1 (1.2%)	0	n/a	0.5 ±-0.3
4p	1 (1.2%)	0	n/a	0.5 ±-0.3

Table 6 EBR and GZR *In Vitro* Susceptibility Data for All GT4 Subtypes Among 81 Isolates Identified from French Patients

GT Subtype	Frequency of GT Subtype among 81 isolates from France sequenced in ref [9] n (%)	Number of GT4 subtype replicons assayed	Range of EBR EC ₅₀ nM	GZR EC ₅₀ for GT1b in Con 1 replicon for reference (nM ± SD)
4a	41 (50.6%)	3	.0002-.003	.003 ± .001
4d	17 (21%)	2	.0004-.0005	.003 ± .001
4f	10 (12.3 %)	1	.0019	.003 ± .001
4k	3 (3.7%)	0	n/a	.003 ± .001
4g	2 (2.5%)	2	.072-.0006	.003 ± .001
4c	2 (2.5%)	0	n/a	.003 ± .001
4q	2 (2.5%)	1	.0005	.003 ± .001
4t	2 (2.5%)	0	n/a	.003 ± .001
4n	1 (1.2%)	0	n/a	.003 ± .001
4p	1 (1.2%)	0	n/a	.003 ± .001

The activity of both EBR and GZR against GT4a and 4d, which appear to be the most prevalent subtypes in France, is comparable to what is seen against GT1b. This similar potency *in vitro* does appear to correlate with *in vivo* efficacy. As demonstrated in [Table 7](#), the treatment response rate of 12 weeks of EBR/GZR in the pooled TN GT4 dataset [10] was similar to the response rate in the in the TN GT1b patients treated in PN035, a randomized, placebo-controlled study that included both cirrhotic and noncirrhotic subjects with HCV GT1, 4, and 6 infection [27].

Table 7 Treatment Response Rates After 12 Weeks of EBR/GZR in Treatment-Naïve Subjects

Regimen	Duration	SVR ₁₂ GT1b (PN035)	SVR ₁₂ GT4 (pooled analysis)
EBR/GZR	12 weeks	129/131 (99%)	54/56 (96%)

The comparable *in vitro* and clinical profiles of EBR and GZR in GT4 and GT1b infection suggest that efficacy of regimens not yet studied in TN GT4 patients may be similar to what was seen in GT1b infection. Accordingly, justification for the 8-week regimen proposed for TN GT4 subjects with F0-F2 fibrosis is based on the high efficacy observed when this same regimen was given to a similar GT1b population. In PN035, one of the treatment arms included an 8-week regimen of EBR and GZR in noncirrhotic TN subjects with GT1b infection and demonstrated that 28/29 TN GT1b subjects with F0-F2 fibrosis achieved SVR₁₂.

4.2.2.2 Rationale for 12-week Regimen of EBR/GZR in TN GT4 (F3-F4)

As seen in [Table 3](#), the efficacy of EBR/GZR was over 96% when given for 12 weeks in TN GT4 subjects enrolled in the phase 2/3 clinical program and there was no difference in TN GT4 subjects with cirrhosis compared to those without cirrhosis supporting continued evaluation of this regimen for GT4 infected subjects in France.

4.2.2.3 Rationale for 12-week Regimen of EBR/GZR in TE GT4 (F0-F4)

As discussed previously, EBR and GZR have comparable in vitro activity against GT4 and GT1b replicons and parallels in treatment response were noted between TN GT4 and GT1b subjects treated with 12 weeks of EBR/GZR. As seen in [Table 8](#), in the pooled Phase 2/3 dataset, TE GT1b subjects responded well to 12 weeks of EBR and GZR while the response rates were lower in a much smaller sample size of TE GT4 subjects. Among the 2 TE GT4 subjects who did not achieve SVR12, one subject relapsed and a second discontinued due to an adverse event (AE) that was not drug related. Similar treatment responses to those observed in TE GT1b infection are expected in TE GT4 subjects and the difference noted above may be modulated by the small sample size of TE GT4 subjects making it difficult to assess the validity of this result. Accordingly, additional work to optimize management of TE GT4 infection, specifically by studying a 12-week RBV free regimen, is warranted.

Table 8 Treatment Response Rates after 12 Weeks of EBR/GZR in Treatment-Experienced Subjects

Regimen	Duration	SVR ₁₂ GT1b	SVR ₁₂ GT4
EBR/GZR	12 weeks	54/56 (96%)	7/9 (78%)

4.2.3 Rationale for Endpoints

4.2.3.1 Efficacy Endpoints

The primary measurement for efficacy in this study is the plasma HCV RNA level. Long term suppression of HCV RNA, typically reported as sustained virologic response (SVR), has been associated with improved outcomes in patients with chronic hepatitis C infection as measured by biochemical and histological remission of liver disease. Most available data suggest that SVR following antiviral therapy reduces the risk of progression to cirrhosis and may prevent the development of severe liver complications and improve survival [28].

The primary evaluation of efficacy in this trial is based on SVR₁₂ (sustained virologic response 12 weeks after the end of all study therapy), the current standard ever since first used for registration of simeprevir and sofosbuvir. Because there is a high degree of concordance between SVR₁₂ and SVR₂₄ [29], SVR₁₂ is used as the primary endpoint for registration of DAAs [13].

Other secondary evaluations of efficacy are based on SVR₂₄ (sustained virologic response 24 weeks after the end of all study therapy).

Detailed definitions for evaluation for SVR are provided later in this section.

4.2.3.1.1 Measurement of HCV RNA

HCV RNA levels in plasma will be measured on blood samples drawn from each subject at various time points prior to, during, and after dosing, as indicated in the Trial Flow Chart (Section 6.0). Samples are collected and processed as per instructions provided by the central laboratory manual (assay type indicated in central laboratory manual).

Results from the sample collected at the screening visit are used to determine eligibility. Samples collected at other time points are used for efficacy analyses. They are also used to identify subjects who meet virologic failure criteria.

The nomenclature detailed in [Table 9](#) will be used when describing HCV RNA levels:

Table 9 Nomenclature for Describing HCV RNA Levels

Abbreviation	Definition	HCV RNA Level
TND	Target not detected	HCV RNA not detected
TD(u)	Target detected but unquantifiable	HCV RNA < LLOQ
TD(q)	Target Detected, quantifiable	HCV RNA \geq LLOQ

4.2.3.1.1.1 Definition of Efficacy Endpoints

Efficacy will be defined at different time points during the trial. Specific endpoints are:

- SVR₁₂ (sustained virologic response 12 weeks after the end of all study therapy). The subject has HCV RNA < LLOQ (either TD[u] or TND) 12 weeks after the end of all study therapy.
- SVR₂₄ (sustained virologic response 24 weeks after the end of all study therapy). The subject has HCV RNA < LLOQ (either TD[u] or TND) 24 weeks after the end of all study therapy.

4.2.3.1.1.2 Definition of Virologic Failure: Non-Response, Rebound, Virologic Breakthrough and Relapse

Lack of efficacy at different time points in the trial will be categorized as:

- Non-response: Subject has HCV RNA detected at end of treatment without HCV RNA $<$ LLOQ on treatment (note that breakthrough is captured below).
- Rebound: Subject has a rebound defined as $>1 \log_{10}$ IU/mL increase in HCV RNA from nadir while on treatment and confirmed from a separate blood draw within 2 weeks.
- Virologic breakthrough: Subject has a confirmed HCV RNA \geq LLOQ (TD [q]) after being $<$ LLOQ previously while on treatment. Confirmation is defined as an HCV RNA \geq LLOQ from a separate blood draw repeated within 2 weeks.
- Relapse: Subject has a confirmed HCV RNA \geq LLOQ (TD [q]) following end of all study therapy, after becoming undetectable (TND) at end of treatment. Confirmation is defined as an HCV RNA \geq LLOQ from a separate blood draw repeated within 2 weeks.

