⁷ For cirrhotic subjects only, imaging is required within 6 months of randomization to evaluate for hepatocellular carcinoma. If liver imaging within 6 months prior to Day 1 is not available, imaging is required during screening.

⁸ Leftover main study plasma will be stored at the end of the study for future biomedical research if the subject consents to FBR.

⁹ If a subject is a confirmed virologic failure during therapy (i.e., rebound, breakthrough), then the sample collection for HCV RNA and viral resistance/biomarker is not needed for the early discontinuation visit.

¹⁰ Blood samples will be collected for HCV viral resistance testing at baseline, virologic failure confirmation visits, and all FU visits after virologic failure confirmation or after early study medication discontinuation if the subject has quantifiable HCV RNA. At the same time points, samples will be collected for proteomics, and metabolomics and other exploratory analysis. Leftover main study plasma will be stored at the end of the study for future biomedical research if the subject consents to future biomedical research.

¹¹ This sample will be drawn for *IL28B* genotyping and for planned analysis of the association between genetic variants in DNA and drug response. Data analysis will be limited to *IL28B* genotyping if the IRB/IEC does not approve of, or if there is a documented law or regulation prohibiting, the planned analysis of the association between DNA variations and drug response. Leftover extracted DNA will be stored for future biomedical research if the subject signs the optional FBR consent.

¹² Blood samples will be collected for HIV RNA and CD4+ T cell counts as part of the screening visit for all subjects; however, these samples will only be processed if the HIV-1 serology result is positive.

¹³ Sites should dispense 3 open-label EBR/GZR blister cards at the Day 1 visit and 2 open-label EBR/GZR blister cards at each remaining dispensing visit. An unscheduled visit must occur to get additional drug if the subject will run out of study drug prior to the next scheduled visit. Subjects should complete study therapy for all study drug as defined by the length of the assigned treatment regimen. If dosing is missed or interrupted (see Section 5.2.2), the assigned study therapy regimen should still be completed.

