7.1.5.1 Screening

Up to 45 days prior to randomization/treatment allocation, potential subjects will be evaluated to determine that they fulfill the entry requirements as set forth in Section 5.1. Verification should be obtained to confirm the subject's cirrhosis status and the subject's fibrosis score must be captured to support secondary data analysis.

Documentation of prior IFN +/- RBV +/- SOF treatment history must include clinic notes or referral letter documenting regimen administered, approximate dates of treatment, approximate date of virologic failure, and a history of laboratory confirmed prior virologic

failure or documented intolerance to allow for one of the following categorizations (if the subject was treated with a PR regimen more than once, the categorization must be based on the most recent round of treatment):

1. HCV Treatment-Naïve: defined as no prior exposure to any interferon, ribavirin, or other approved or experimental HCV-specific direct-acting antiviral agent.
2. HCV Treatment-experienced: defined as any prior treatment with an IFN regimen (IFN or peg-IFN +/- RBV) or sofosbuvir (SOF) + RBV or SOF + peg-IFN + RBV that did not result in a sustained virologic response (SVR)

All TE patients will be classified into one of the following categories:

- I. Prior On-Treatment Failures (may be one or more of the following):
 - i. Non-Responder: Subject has HCV RNA detected at end of prior treatment without HCV RNA <LLOQ on treatment.
 - ii. Null Responder: <2 log₁₀ IU/mL reduction in HCV RNA after at least 12 weeks of a IFN regimen OR <1 log₁₀ IU/mL reduction in HCV RNA after 4 weeks and discontinued therapy prior to treatment-week 12.
 - iii. Breakthrough: Subject has a confirmed HCV RNA \geq LLOQ [TD(q)] while on prior treatment after being <LLOQ previously.
 - iv. Partial Responder: \geq 2 log₁₀ IU/mL reduction in HCV RNA after at least 12 weeks of treatment, but not achieving HCV RNA target not detected at end-of-treatment, with prior regimen.
- II. Relapser: HCV RNA target not detected at end-of-treatment after prior regimen, but HCV RNA quantifiable (\geq LLOQ) during follow-up.
- III. Intolerant to Prior Regimen: \geq 4 weeks of prior regimen and no more than 80% of treatment duration:
 1. \leq 20 weeks for a 24 week treatment regimen
 2. \leq 40 weeks for a 48 week treatment duration

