7.1.5.5 Follow-Up Visits

At the completion of study therapy subjects will return to the study site for follow-up visits at 4, 12, and 24 weeks after the last dose of study drug.

Subjects who discontinue because they have met criteria for virologic failure (Section 4.2.3.1.1.2) while on study therapy should complete an Early Discontinuation Visit as outlined in the Trial Flow Chart (Section 6.0), and return to the study site for follow-up visits at 4, 12, and 24 weeks following confirmation of virologic failure. Subjects who meet the virologic failure criterion for relapse (HCV RNA \geq LLOQ following the end of all study therapy, after becoming undetectable [TND] at the end of treatment) will return to the study site for the remainder of their follow-up visits (e.g., 4, 12, and 24 weeks) as outlined in the Trial Flow Chart (Section 6.0).

Subjects who discontinue for reasons other than virologic failure should complete an Early Discontinuation Visit as outlined in the Trial Flow Chart and return to the study site for follow-up visits at 4, 12, and 24 weeks following the discontinuation of treatment.

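### A subject at TD(u) at end of treatment whose virus returns in follow-up is not a relapse and, on the likelier reading of breakthrough, has no failure category and no place in the Resistance Analysis population

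*Combined protocol and SAP*

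**What the plan says.** Table 9 and the SVR definitions in Section 4.2.3.1.1.1 treat TD(u) and TND alike: both are below the LLOQ and both count as response. Section 4.2.3.1.1.2 then lists four kinds of virologic failure.

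- **Relapse** is confirmed HCV RNA ≥ LLOQ "following end of all study therapy, after becoming undetectable (TND) at end of treatment". Section 7.1.5.5 repeats the condition: "after becoming undetectable [TND] at the end of treatment".
- **Non-response** begins "Subject has HCV RNA detected at end of treatment without HCV RNA" and goes on to require that no on-treatment result was below the LLOQ.
- **Rebound** is a confirmed rise of more than 1 log10 from nadir during treatment.
- **Breakthrough** is a confirmed result ≥ LLOQ after a result below "LLOQ previously while on treatment". The bullet does not settle whether the on-treatment qualifier belongs to the new quantifiable result or to the earlier one.

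Two other places bear on that ambiguity. Flow-chart footnote 9 reads "If a subject is a confirmed virologic failure during therapy (i.e., rebound, breakthrough". The prior-treatment definition of breakthrough in Section 7.1.5.1 ties the quantifiable result to the treatment period: "while on prior treatment after being <LLOQ previously".

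The prior-treatment scheme in Section 7.1.5.1 also builds relapse on TND ("Relapser: HCV RNA target not detected at end-of-treatment after prior regimen"). It has a Partial Responder category for subjects "but not achieving HCV RNA target not detected at end-of-treatment, with prior regimen" and a residual unclassified category. The on-study list has neither.

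The labels are used in three places. Section 8.6.1 summarises rates of the four categories. Section 8.5.1 limits the Resistance Analysis (RA) population to FAS subjects who reached SVR12 or met a Section 4 failure criterion. Section 4.2.3.1.2 requires post-failure resistance testing when a failure criterion is met and virus exceeds 1000 IU/mL.

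**The concern.** The success and failure definitions do not meet. A subject can be below the LLOQ at end of treatment (TD(u)), be confirmed quantifiable in follow-up, fail SVR12, and still match no failure category.

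Two outputs are exposed. First, the relapse summary omits a subject who was below the LLOQ at the end of therapy and was quantifiable afterwards. Second, secondary objective 3 and its endpoint concern emergent RAVs in subjects who fail to achieve SVR, but the set used to analyse them admits non-SVR subjects only through a failure label. In arms of 50 and 70 with high expected response, post-treatment failures will be few, so losing one from the emergence analysis would be noticeable.

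**Working it through.** **Inputs.** The four failure definitions (4.2.3.1.1.2); the classes TND, TD(u) and TD(q) (Table 9); the RA rule (8.5.1); planned arm sizes of 50 and 70 (8.9.1). The plan states no relapse rate, so there is no such figure to reproduce.

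**Step 1: one subject against each definition.** Take TD(u) at end of treatment and confirmed HCV RNA ≥ LLOQ in follow-up.
- Relapse: no, because the end-of-treatment result is not TND.
- Non-response: no, because a result below the LLOQ occurred at the Week 8 or Week 12 visit, which the flow chart places in the treatment period.
- Rebound: no, because the rise came after treatment.
- Breakthrough: no if the quantifiable result must be on treatment; yes if only the earlier result below the LLOQ must be.

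**Step 2: all paths.** Cross one earlier on-treatment result (TND, TD(u), TD(q)) with the end-of-treatment result (same three), each followed by HCV RNA ≥ LLOQ in follow-up: 3 × 3 = 9 paths. Every quantifiable result is assumed confirmed and the end-of-treatment visit is counted as on treatment. Rebound is set aside here and taken up below.

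| End of treatment | Paths | Breakthrough on treatment only | Breakthrough may also follow treatment | After both wording changes |
|---|---|---|---|---|
| TND | 3 | relapse | relapse and breakthrough | relapse |
| TD(u) | 3 | no label | breakthrough only | relapse |
| TD(q), earlier TND or TD(u) | 2 | breakthrough | breakthrough | breakthrough |
| TD(q), earlier TD(q) | 1 | non-response | non-response | non-response |

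- On-treatment reading: 3 of 9 paths have no label; relapse covers 3 of 9.
- Wider reading: none unlabelled, but 3 of 9 carry both relapse and breakthrough; relapse still covers only 3 of 9.
- Relapse wording changed alone, wider reading: 3 + 3 = 6 of 9 carry both labels.
- Both changes: none unlabelled; relapse covers 3 + 3 = 6 of 9 and no longer overlaps with breakthrough.

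Rebound can add a second label to any of the three TD(q)-ending paths if the on-treatment rise exceeds 1 log10 and is confirmed. That overlap exists now and remains after the changes. These are counts of paths, not frequencies of subjects.

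**Step 3: what follows from having no label.** With SVR12 not reached and no Section 4 criterion met, the subject fails both entry routes to the RA population. The failure-based trigger in 4.2.3.1.2 is not met. The separate route for early discontinuers in that section does not cover a treatment completer.

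**Step 4: illustration of size.** Clopper-Pearson 95% limits are Beta⁻¹(0.025; x, n−x+1) and Beta⁻¹(0.975; x+1, n−x). Assume three confirmed post-treatment failures in an arm. Section 8.6.1 gives no denominator, so the first two rows assume all subjects in the arm.

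| Denominator | None at TD(u) | One of the three at TD(u) |
|---|---|---|
| Arm 1, all 50 | 3/50 = 6.0% (1.3 to 16.5) | 2/50 = 4.0% (0.5 to 13.7) |
| Arm 2, all 70 | 3/70 = 4.3% (0.9 to 12.0) | 2/70 = 2.9% (0.3 to 9.9) |
| Arm 1, only those TND at end of treatment (other 49 all TND) | 3/50 = 6.0% (1.3 to 16.5) | 2/49 = 4.1% (0.5 to 14.0) |

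The upper limits 16.5 and 13.7 (n = 50) and 12.0 and 9.9 (n = 70) match Table 18. FAS SVR12 in Arm 1 is 47/50 = 94.0% (83.5 to 98.7) in every case, matching Table 17, because HCV RNA ≥ LLOQ is non-response whatever the label (Table 15).

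**The case against.** **The breakthrough wording can be read the other way.** In the bullet, the on-treatment qualifier stands next to the earlier result below the LLOQ. On that reading the subject is a breakthrough, enters the RA population and is tested. This stands as a condition on the resistance consequence. It does not rescue the scheme: footnote 9 and Section 7.1.5.1 point to the on-treatment reading, and under the wider one every relapse is also a breakthrough. The subject is missing from the relapse summary either way.

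**TND may be deliberate.** It appears in 4.2.3.1.1.2, 7.1.5.5 and the prior-treatment Relapser category, and against that definition the relapse rate is correct. This is fair: the rate is low only relative to a definition based on the LLOQ. But the documents give no reason for asking more at end of treatment than SVR itself asks, and only the prior-treatment scheme has somewhere to put the remaining cases.

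**The end-of-treatment sample may follow the last dose.** The Week 8 and Week 12 window is −7 to +14 days. A subject who was TD(q) until then and first TD(u) in a late sample could be read as a non-response. So the path from TD(q) to TD(u) is unlabelled only if that sample counts as on treatment.

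**Testing may happen anyway.** Resistance plasma is marked at all three follow-up visits (subject to footnote 10), Section 12.5 budgets 6 mL at each, and leftover plasma may be tested. Section 8.6.3 also speaks of resistance testing for all subjects, which may mean baseline only. A reader might infer that the sample is lost; the documents do not support that. What can be lost is the requirement to test and RA membership, and optional testing restores neither.

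**Conclusion.** The point holds as a gap in classification, of low severity. It rests on breakthrough being an on-treatment event and on the end-of-treatment sample counting as on treatment. Given both, a treatment completer at TD(u) with confirmed later HCV RNA ≥ LLOQ who fails SVR12 has no failure category, is outside the RA population and does not trigger failure-based testing, which does not fit secondary objective 3. Without the first condition, what remains is the omission from the relapse summary and the double labelling of every relapse.

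The size is unknown and may be zero, since the documents give no frequency of TD(u) at end of treatment. The figures above rest on an assumed three failures.

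Three stronger inferences are not supported:
- That the main efficacy results are affected. FAS SVR12 and SVR24 depend on HCV RNA alone, and the relapse rate is a descriptive summary, not a listed endpoint.
- That the mFAS analysis is affected. This would need documented virologic failure in 8.6.1 to mean only the four categories, which the text does not say.
- That rewording gives every subject exactly one label. The overlap of rebound with breakthrough or non-response for subjects at TD(q) at end of treatment remains.

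**What to change.** 1. In 4.2.3.1.1.2 and 7.1.5.5, define on-study relapse as confirmed HCV RNA ≥ LLOQ after the end of all study therapy, following HCV RNA < LLOQ (TD(u) or TND) at end of treatment.
2. In the breakthrough bullet, state that the result ≥ LLOQ occurs on treatment. Both changes are needed: with the first alone, the wider reading would still label every relapse twice.
3. In 7.1.5.1, note that the prior-treatment Relapser category keeps its own TND-based definition.

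Every path to post-treatment HCV RNA ≥ LLOQ then carries at least one failure label. The changes concern classification for analysis and leave the on-treatment discontinuation rule in 5.8.1 as it stands. They do not address the rebound overlap, or the separate RA exclusion of subjects who left the study for reasons other than virologic failure.

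The cost is a phrase in two places, one clarification and one note. The relapse rate may read slightly higher, and on-study relapse will no longer match the prior-treatment category.
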